1. INTRODUCTION

The purpose of this statistical analysis plan (SAP) is to describe the procedures and the statistical methods that will be used to analyze the data and report results for study JNJ-74494550-AML-2001.

JNJ-74494550-AML-2001 is an open-label, 2-part, multicenter, Phase 2 study to evaluate efficacy and safety of 2 dose levels of cusatuzumab (10 mg/kg and 20 mg/kg) in combination with azacitidine in participants with previously untreated acute myeloid leukemia (AML) who are not eligible for intensive chemotherapy.

1.1. Study Objectives

1.1.1. Primary Objective

The primary objective is to determine the complete response (CR) rate per ELN 2017 (Dohner 2017) of 2 dose levels of cusatuzumab in combination with azacitidine.

1.1.2. Secondary and Exploratory Objectives

Secondary objectives are to evaluate the following:

- Rate of CRh
- Rate of CR + CRh
- Rate of CRi
- Overall response rate (ORR) = CR + CRh + CRi
- Rate of CR without MRD
- Time to response, defined as time from randomization/enrollment to achieving the first response of CRi, CRh, or CR
- Duration of response, defined as time from achieving first response of CRi, CRh, or CR to disease relapse, progression or death of any cause
- Safety profile of adverse events (AE) and serious adverse events (SAE)
- Transfusion independence (TI), defined as having a period of at least 56 consecutive days with no red blood cell or platelets transfusion between randomization and the last dose of study drug + 30 days
- Pharmacokinetics (PK) of cusatuzumab alone and in combination with azacitidine
- Immunogenicity/anti-drug antibody of cusatuzumab alone and in combination with azacitidine

Exploratory objectives are to summarize the following:

- Progression-free survival (PFS), defined as the time from randomization (part 1) or enrollment (part 2) to progressive disease, relapse from CR/CRh/CRi, or death from any cause, whichever occurs first
- Overall survival (OS), defined as the time from randomization (part 1) or enrollment (part 2) to death from any cause

- Exploratory biomarkers including baseline level of CD70+ blasts, CD70+ LSC, sCD27, NK cells: to assess the pharmacodynamics and to explore biomarkers predictive of clinical response
- PROs using the FACT-Leu and EQ 5D 5L

1.2. Trial Design

The study consists of 2 sequential parts, Part 1 and Part 2. The purpose of Part 1 is to select a dose level (10 mg/kg or 20 mg/kg) based on the totality of the data, including CR rate and other efficacy endpoints, PK, biomarkers, and safety. The purpose of Part 2 is to further evaluate and confirm the efficacy and safety of the combination therapy at the selected dose of cusatuzumab.

During Part 1, participants are randomly assigned in a 1:1 ratio, with stratification by types of AML (de novo versus secondary AML) and ECOG score (0-1 versus 2), in one of the 2 treatment groups:

- Group A: Azacitidine 75 mg/m² SC or IV on Day 1 through Day 7, cusatuzumab 10 mg/kg IV on Day 3 and Day 17 of each 28-day cycle
- Group B: Azacitidine 75 mg/m² SC or IV on Day 1 through Day 7, cusatuzumab 20 mg/kg IV on Day 3 and Day 17 of each 28-day cycle

A 3-stage monitoring approach, as the statistical guidance, is utilized in Part 1 to select a dose level (see Section 1.5, Interim Analysis). The cumulative number of participants for each dose group at each of the 3 stages is 15, 30, and 50, respectively. Available data will be evaluated after the last enrolled participant has been treated for 4 cycles with the combination therapy.

Additionally, after 5 participants have enrolled on each arm and been treated for 2 cycles, cumulative safety data will be evaluated by the DRC to ensure continued study treatment is safe.

For Part 2, the treatment group to be studied will be dependent upon the results from Part 1. Approximately 100 participants are included for the selected treatment group from Parts 1 and 2 combined. A formal interim analysis of the primary endpoint, CR rate, is planned during Part 2 to include 80 participants from the selected dose group. The final analysis will be based on 100 participants.

[figure not shown]
Upon 1 dose level being selected to continue, ongoing participants who are not receiving the selected cusatuzumab dose may switch to that dose. This will be following review and approval of the selected dose by the Data Review Committee (DRC) (see below).

A diagram of the study design is provided in [Figure 1](#).

A Data Review Committee (DRC) will be established to review cumulative safety and efficacy data at planned interim time points, to ensure participants' safety, to evaluate efficacy results, and to make recommendations on dose selection, study continuation, and other study conduct related

matters. There will be a separate DRC charter that describes the composition of the DRC, and the role and responsibilities of the DRC members.

Figure 1.

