Part 1 of the study utilizes a 3-stage monitoring approach as the statistical guidance to select a dose schedule (see Section 9.5, Interim Analysis). The cumulative number of participants for each dose group at each of the 3 stages are 15, 30, and 50, respectively. Response will be based on all evaluations up to the time point when the last participant is treated for a minimum of 3 cycles with combination therapy (cusatuzumab + azacitidine). At each stage, available data of efficacy, safety, pharmacodynamics, and biomarkers will be evaluated by a Data Review Committee (DRC) to determine if either or both of these treatment groups should continue into the next stage of Part 1, and by the end of Part 1 (n=50/group), to select 1 dose schedule to be continued into study Part 2. The DRC will be formed prior to the first participant being enrolled in the trial and will remain in place until the conclusion of the trial. Enrollment does not pause at each stage. Refer to Committees Structure in Appendix 3 (Section 10.3), Regulatory, Ethical, and Study Oversight Considerations for details.

If, based upon the totality of the data, 1 treatment group is considered to be less effective at any stage of Part 1, then that treatment group will be closed to enrollment. Upon 1 dose level being selected to continue, the DRC may determine to switch ongoing participants to treatment with the dose level selected. If 1 dose group is determined at Stage 1 or Stage 2 not to continue, the other dose group will be continued into study Part 2 directly without further evaluations in Part 1. Enrollment will continue at each of the above 3 stages while efficacy and safety data are accumulated and evaluated.

Additionally, after 5, 15, 30, and 50 participants have enrolled on each arm, respectively, and been treated for 3 cycles, cumulative safety data will be evaluated by the DRC to ensure continued study treatment is safe.

Part 2:

For Part 2, the treatment group to be studied will be dependent upon the results from Part 1. At the end of Part 1, all available data will be evaluated by the DRC to select 1 of the cusatuzumab treatment groups for further evaluation in Part 2.

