6.5.3. Subsequent Anticancer Therapy

Data on subsequent anticancer therapy (AML directed therapy, radiotherapy, surgery, or hematopoietic stem cell transplant) administered after the last dose of study intervention should be documented in the eCRF (including start and end date and best response, if available) until the clinical cutoff for the primary CSR analysis.

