9.5. Interim Analyses

For each analysis (3 stages in Part 1 and the formal interim and final analysis in Part 2), the data cutoff will be the time point when the last participant in the respective analysis has been treated for a minimum of 3 cycles (Part 1) or 4 cycles (Part 2) of the combination therapy.

NOTE: Part 2 of the study will not be conducted because further development of this regimen (cusatuzumab in combination with azacitidine) in patients with unfit AML will not be pursued due to the evolving treatment landscape in AML.

Study Part 1

Part 1 of the study consists of 3 stages of monitoring to select a dose schedule. The cumulative number of participants for each dose group at each of the 3 stages are 15, 30, and 50, respectively. At each stage, each dose group's response rate will determine independently (without formal statistical comparison to the other group) if that dose group will be stopped or continued into the next stage or into study Part 2. Only 1 dose group will be selected for Part 2. The statistical criteria for such a determination will be based on the number (and percentage) of participants in each dose group achieving CR.

The purpose of the 3-stage monitoring in Part 1 is to select, or to eliminate a dose, which will be based on the Pocock beta-spending function with an overall beta level of 10% allocated to the 3 stages with respective and cumulative sample sizes of 15 (30%), 30 (60%), and 50 (100%) participants per group. Per this approach, the statistical decision criteria and corresponding inferences are summarized in Table 7, where 2 possible outcomes resulting in a stop or continuation decision, respectively, are presented for each stage.

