10.11. Appendix 11: Protocol Amendment History

The Protocol Amendment Summary of Changes Table for the current amendment is located directly before the Table of Contents (TOC).

Amendment 3 (30 September 2021)

Overall Rationale for the Amendment: After 22 Oct 2021 (after the primary endpoint analysis had been completed), subjects who are still benefiting from study treatment can continue to receive study treatments and will have a reduced schedule of assessments.

Section Number and Name	Description of Change	Brief Rationale
1.3 Schedule of Activities (SoA) Table 1	Note was added indicating that after 22 Oct 2021, subjects will no longer be treated and assessed per Table 1 but will follow reduced schedule of assessments per Table 1A.	Modified timing of blood sample collection/analyses and assessments to reduce burden for ongoing study participants
1.3 Schedule of Activities (SoA) Table 1A	
A new SoA table was added limiting the number of assessments.
 
Minimal residual disease analysis is included in Table 1A. Bone marrow: every 4 cycles following CR and every 2 cycles following complete response with incomplete blood count recovery (CRi)/ complete response with partial hematological recovery (CRh) (collected between Day 21 up to and including Day 1 of the next cycle). Whole Blood: Every 2 cycles following CR/CRi/CRh on Day 1.
 
A note was added that for participants who discontinue study treatment without disease progression, disease evaluations should continue with the same frequency as during study treatment until disease progression or start of subsequent therapy, whichever occurs first.
	
Synopsis; 1.3 Schedule of Activities (SoA); Table 2; Table 3; Table 4; Table 5; Section 4.1	Note was added that after 22 Oct 2021, blood samples for pharmacodynamic, biomarker, and pharmacokinetic analysis will not be collected.	
Throughout the protocol	Minor grammatical, formatting, or spelling changes were made.	To provide clarity.

Amendment 2 (19 August 2020)

Overall Rationale for the Amendment: This amendment removes Part 2 of the study and addresses feedback from the investigators on the timing of disease assessments and use of anti-infective prophylaxis.

Section Number and Name	Description of Change	Brief Rationale

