3. Objectives and Endpoints	Clarified the definition of time to response and duration of response; added the secondary endpoint of transfusion independence and its definition	To provide further clarification of the existing text Added relevant endpoint for AML studies
10.3 Appendix 3: Data Review Committee	Added language regarding membership and activities of the Data Review Committee	To further clarify membership and activities of the Data Review Committee
4.1 Overall Design; 9.5 Interim Analyses	Changed timing of data for DRC review to minimum of 3 cycles for Part 1 and 4 cycles for Part 2 from 4 cycles per participant; added language regarding activities of the DRC	To provide further clarification of the existing text

Section number and Name	Description of Change	Brief Rationale
5.1. Inclusion Criteria	Clarified co-morbidity inclusion criterion; added hydroxyurea and changed low dose cytarabine to dose of cytarabine (1-2g/m ²) to exceptions for treatment; renumbered inclusion criteria with 3 bulleted items from criteria 2 in the original protocol placed as criteria 3 to 5; clarified contraceptive language; removed age restriction for definition of “postmenopausal”; added language to include legally acceptable representative in understanding the ICF; added criteria related to donation of eggs or sperm; added criteria related to fathering a child.	To manage hyperleukocytosis; to clarify inclusion criteria
5.2. Exclusion Criteria	Removed language defining genetic marker for APL; clarified that the immune suppressive agent administration should be terminated before the Cycle 1 Day 3 cusatuzumab dose; removed “untreated” from systemic infection exclusion criterion; removed “if tested” from HIV related exclusion criteria because all are tested; added instructions for treatment of adrenal insufficiency; added criterion to exclude women who are breastfeeding; modified criteria related to prior/current other malignancies; added criterion to exclude participants who received live attenuated vaccines; clarified criterion with regard to hepatitis B and C infection; clarified exclusion for major surgery 4 weeks prior to initiation of study.	Corrected day to match cusatuzumab dosing; clarified exclusion criteria; added exclusion criteria
5.3 Lifestyle Considerations	Added statement that male participants should inform fertile female partners to use effective methods of birth control.	To further clarify contraception instructions for male participants

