1.5. Interim Analyses

For each analysis (3 stages in Part 1 and the formal interim and final analysis in Part 2), the data cutoff will be the time point when the last participant in the respective analysis has been treated for a minimum of 3 cycles (Part 1) or 4 cycles (Part 2) of the combination therapy.

Study Part 1

Part 1 of the study consists of 3 stages of monitoring to select a dose schedule. The cumulative number of participants for each dose group at each of the 3 stages are 15, 30, and 50, respectively. At each stage, each dose group's response rate will be determined independently (without formal statistical comparison to the other group) if that dose group will be stopped or continued into the next stage or into study Part 2. Only 1 dose group will be selected for Part 2. The statistical criteria for such a determination will be based on the number (and percentage) of participants in each dose group achieving CR.

The purpose of the 3-stage monitoring in Part 1 is to select, or to eliminate a dose, which will be based on the Pocock beta-spending function. The overall beta level is chosen as 10%, allocated to the 3 stages with respective and cumulative sample sizes of 15 (30%), 30 (60%), and 50 (100%) participants per group; the corresponding nominal significance level (calculated against the alternative hypothesis of 35% CR rate) are 0.04157, 0.04618, and 0.05632. Per this approach, the statistical decision criteria and corresponding inferences are summarized in [Table 1](#), where 2 possible outcomes resulting in a stop or continuation decision are presented for each stage.

The statistical criteria shown in [Table 1](#) ensure that the false negative error rate (ie, the probability of a stopping decision, when the true CR rate is $\geq 35\%$) is $\leq 6\%$ at any stage; or equivalently, the upper limit of the 1-sided $>94\%$ confidence interval (CI) of the observed CR rate is $<35\%$ (which means that a CR rate of 35% or greater has been statistically ruled out). It's important to control the false negative error rate at a low level when the number of participants is small to ensure that a stopping decision will not be made unless it is statistically convincing that a CR rate of $\geq 35\%$ has been ruled out. Since all the analyses in study Part 1 are futility evaluations without the intention to stop for efficacy, the overall type I error of the entire study is not inflated.

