1.6. Changes of Study Conduct and Planned Analyses

The study did not proceed into Part 2 per decision by study Sponsor and the DRC upon completion of the analyses in all 3 stages in study Part 1. Data from study Part 1 will be summarized with descriptive statistics without formal comparison or hypothesis testing.

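### Does the SAP's 4-cycle versus 3-cycle mismatch leave the data cut for the Part 1 CR rate in doubt?

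*SAP*

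**What the plan says.** Four current passages time the Part 1 evaluation.

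- SAP 1.2, in the paragraph on the three monitoring stages: "Available data will be evaluated after the last enrolled participant has been treated for 4 cycles with the combination therapy".
- SAP 1.5: the cutoff comes when "the last participant in the respective analysis has been treated for a minimum of 3 cycles (Part 1) or 4 cycles (Part 2").
- Protocol 9.5 has the same rule and says what it covers: "For each analysis (3 stages in Part 1 and the formal interim and final analysis in Part 2), the data cutoff".
- Protocol 4.1, for Part 1: "Response will be based on all evaluations up to the time point when the last participant is treated for a minimum of 3 cycles".

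SAP 1.6 records that the study stopped after all three Part 1 stages had been analysed, and then says: "Data from study Part 1 will be summarized with descriptive statistics without formal comparison or hypothesis testing". SAP 4.1 asks for the CR count, percentage and 95% CI by arm and combined, with no data cut. Protocol 8.1 scores best response over the whole of treatment. Protocol 6.5.3 collects later anticancer therapy "until the clinical cutoff for the primary CSR analysis", a date that is not defined elsewhere.

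**The concern.** CR rate is the primary endpoint, and with Part 2 dropped the Part 1 rate is the study's main result. A best-response rate with no end date can stay level or rise as follow-up lengthens, but it cannot fall. If the SAP gives two cut times for Part 1 and ties the reported rate to neither, a reader cannot tell from the SAP how long non-responders were followed. In an open-label study whose stage results are known, an open cut might also look like room to choose.

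The timing adds to the worry. Protocol 2.2.2.1 gives a median time to first response of 14 weeks in the earlier study of the combination. That lies between 3 cycles (12 weeks) and 4 cycles (16 weeks), so some responses might still be arriving at the cut.

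**Working it through.** **1. Does any design figure depend on the cut?** Start with the plan's own Stage 3 boundary (Protocol Table 7, SAP Table 1): Wilson upper bound, one-sided 94%, n = 50, z = 1.555.

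Upper bound = [p + z²/2n + z·√(p(1−p)/n + z²/4n²)] / (1 + z²/n)

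- 12/50: (0.240 + 0.0242 + 0.0970) / 1.0483 = 34.4%, as stated (stop).
- 13/50: (0.260 + 0.0242 + 0.0994) / 1.0483 = 36.6%, as stated (continue).

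The other ten upper bounds in the table also reproduce. For Part 2, the nominal p-value limits translate to at least 25/80 or at least 29/100 CRs. These give exact power 0.920 and type 1 error 0.0231, in line with the stated >90% and <2.5%. The inputs throughout are counts, sample sizes and error levels. Follow-up time is not among them, so neither cut alters any of these figures.

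**2. How far apart are the cuts?** 3 × 28 = 84 days (12 weeks) and 4 × 28 = 112 days (16 weeks), a difference of 28 days.

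**3. What does the last participant gain?** Protocol Table 1 schedules disease evaluations at the end of odd cycles, about days 28, 84 and 140. By day 84 there are two, and by day 112 there are still two. The Cycle 3 window runs to Day 1 of Cycle 4 (day 85), so a marrow taken on its last day sits at the edge of the 3-cycle cut. The cut is a minimum, which leaves room for it.

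**4. What do earlier participants gain?** Evaluations are 56 days apart. With evenly staggered entry (an assumption), 28/56 = one half of those still evaluated every other cycle would have one more evaluation by the later cut. It can change the rate only for someone not yet in CR.

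**5. Size.** The documents give neither accrual nor the distribution of time to CR, so both are assumed. A simulation (40,000 trials per scenario, 50 per arm, eventual CR rate taken as 35%) covered 16 combinations: accrual of 2 or 4 per arm per month; exponential or Weibull (shape 2) time to CR; median 12 or 14 weeks; CR counted when it occurs or at the next evaluation. Moving the cut from 12 to 16 weeks raised the observed rate by 0.64 to 1.55 points. In participants: 0.0064 × 50 = 0.3 to 0.0155 × 50 = 0.8 per arm. One participant is 1/50 = 2 points.

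For comparison, 17/50 = 34% has an exact 95% CI of 21.2% to 48.8%, a width of 27.6 points. The largest shift is 1.55/27.6, about 6% of that width.

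**6. Which cut governs?** Three of the four passages agree on 3 cycles, and SAP 1.2 itself refers to SAP 1.5 for the monitoring rules. The amendment history explains the odd one out; Amendment 1 reads: "Changed timing of data for DRC review to minimum of 3 cycles for Part 1 and 4 cycles for Part 2". The SAP 1.2 sentence matches the rule before that change.

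**7. Is the reported rate without a cut?** Protocol 9.2 and SAP 1.4 plan up to 50 per group in Part 1, and Stage 3 is 50 per group. Stage 3 is therefore the whole planned Part 1 sample, and Protocol 4.1 states the response rule that goes with it.

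**The case for a change.** The strongest case for a change is that the SAP contradicts the section it points to. Reading a minimum of 3 as allowing 4 does not remove the conflict, because SAP 1.5 assigns 4 cycles to Part 2. Nor does any passage say that the Stage 3 cut is the reporting cut. Treatment and evaluations continued after the stages, so a later report cutoff is possible. On the same assumptions, a cut at the last participant's end-of-Cycle-5 evaluation (20 weeks) would add 1.0 to 3.3 points over the 3-cycle cut.

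The wording conflict stands, and so does the silence of SAP 4.1. The inference that the analysis must change does not. Even 3.3 points is 0.033 × 50 = 1.7 participants per arm, well inside the interval above. The 14-week median comes from 12 participants, covers any response rather than CR alone, and followed a monotherapy lead-in, so it is weak evidence of late CRs here. Adding a CR rate at Cycle 5 would be a preference: neither document sets that threshold, and with stage results known it would be post hoc and could only raise the estimate. The undefined cutoff in Protocol 6.5.3 governs collection of subsequent therapy, not CR. As for freedom to choose a cut, the rationale for Amendment 3 places the 22 Oct 2021 changeover "after the primary endpoint analysis had been completed".

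SAP 1.2 and Protocol 4.1 also disagree on the first DRC safety review (2 versus 3 cycles). Those passages need reconciling for the record, but they have no bearing on the CR rate.

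**Conclusion.** No change to the planned analysis follows. The 4-cycle sentence in SAP 1.2 is a clerical carry-over, outweighed by SAP 1.5 and by Protocol 4.1 and 9.5. It affects no boundary, power figure, sample size or completed stage decision. Its effect on the Part 1 CR rate is 0.64 to 1.55 points, under one participant per arm, on assumed accrual, assumed time to CR and an assumed eventual rate of 35%. The finding that the last participant has the same two scheduled evaluations needs none of those assumptions, only cycles that run to schedule.

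The absence of a cut in SAP 4.1 is a gap that analysts can fill sensibly. The natural choice is the Stage 3 cut, and the study report would be expected to state its data cutoff and minimum follow-up as a matter of course. Because Part 1 is descriptive, with no test or comparison between arms, nothing further depends on it.
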